|                                                             | 
Measured 180 days prior to and including day of drug initiation in any diagnosis position and in an inpatient care setting
 
Gastrointestinal bleeding:
 
ICD-9 Dx:
531.0x gastric ulcer w/ hemorrhage,
531.2x gastric ulcer w/ hemorrhage and perforation
531.4x
531.6x chronic / unspecified ulcer w/ hemorrhage
532.0x, 532.2x, 532.4x, 532.6x, 533.0x, 533.2x, 533.4x, 533.6x,
534.0x, 534.2x, 534.4x, 534.6x, 562.0x, 562.1x, 568.8x, 569.3x, 569.8x
578.x Gastrointestinal hemorrhage
 
ICD-10 Dx:
K25.0x, K25.2x, K25.6x, K26.0x, K26.2x, K26.4x, K26.6x, K27.0x, K27.2x, K27.4x, K27.6x,
K28.0x, K28.2x, K28.4x, K28.6x, K55.21, K57.xx, K62.5x, K63.1x, K63.81, K66.1x, K92.0x,
K92.1x, K92.2x
 
ICD-9 Px: 44.43
ICD-10 Px: 0W3PBZZ
 |  |  |
| • 2 months                                                  |                                                                                                                                                                                                                                                                                                                                                                                                                                                                                                                                                                                                                                                                                                                                                                                                                            |  |  |

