| 534.4  | CHRONIC OR UNSPECIFIED GASTROJEJUNAL ULCER WITH HEMORRHAGE                                                  |
| 534.4  | CHRONIC OR UNSPECIFIED GASTROJEJUNAL ULCER WITH HEMORRHAGE WITHOUT OBSTRUCTION                              |
| 534.41 | CHRONIC OR UNSPECIFIED GASTROJEJUNAL ULCER WITH HEMORRHAGE WITH OBSTRUCTION                                 |
| 534.6  | CHRONIC OR UNSPECIFIED GASTROJEJUNAL ULCER WITH HEMORRHAGE AND PERFORATION                                  |
| 534.6  | CHRONIC OR UNSPECIFIED GASTROJEJUNAL ULCER WITH HEMORRHAGE AND PERFORATION WITHOUT OBSTRUCTION              |
| 534.61 | CHRONIC OR UNSPECIFIED GASTROJEJUNAL ULCER WITH HEMORRHAGE AND PERFORATION WITH OBSTRUCTION                 |
| 562.02 | DIVERTICULOSIS OF SMALL INTESTINE WITH HEMORRHAGE                                                           |
| 562.03 | DIVERTICULITIS OF SMALL INTESTINE WITH HEMORRHAGE                                                           |
| 562.12 | DIVERTICULOSIS OF COLON WITH HEMORRHAGE                                                                     |
| 562.13 | DIVERTICULITIS OF COLON WITH HEMORRHAGE                                                                     |
| 568.81 | HEMOPERITONEUM (NONTRAUMATIC                                                                                |
| 569.3  | HEMORRHAGE OF RECTUM AND ANUS                                                                               |
| 569.83 | PERFORATION OF INTESTINE                                                                                    |
| 569.85 | ANGIODYSPLASIA OF INTESTINE WITH HEMORRHAGE                                                                 |
| 569.86 | DIEULAFOY LESION (HEMORRHAGIC) OF INTESTINE                                                                 |
| 578    | HEMATEMESIS                                                                                                 |
| 578.1  | BLOOD IN STOOL                                                                                              |

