## Appendix A

|        |                                                                                             |
|--------|---------------------------------------------------------------------------------------------|
| I61.2  | Nontraumatic intracerebral hemorrhage in hemisphere, unspecified                            |
| I61.3  | Nontraumatic intracerebral hemorrhage in brain stem                                         |
| I61.4  | Nontraumatic intracerebral hemorrhage in cerebellum                                         |
| I61.5  | Nontraumatic intracerebral hemorrhage, intraventricular                                     |
| I61.6  | Nontraumatic intracerebral hemorrhage, multiple localized                                   |
| I61.8  | Other nontraumatic intracerebral hemorrhage                                                 |
| I61.9  | Nontraumatic intracerebral hemorrhage, unspecified                                          |
| I62.00 | Nontraumatic subdural hemorrhage, unspecified                                               |
| I62.01 | Nontraumatic acute subdural hemorrhage                                                      |
| I62.02 | Nontraumatic subacute subdural hemorrhage                                                   |
| I62.03 | Nontraumatic chronic subdural hemorrhage                                                    |
| I62.1  | Nontraumatic extradural hemorrhage                                                          |
| I62.9  | Nontraumatic intracranial hemorrhage, unspecified                                           |
| K25.0  | Acute gastric ulcer with hemorrhage                                                         |
| K25.2  | Acute gastric ulcer with both hemorrhage and perforation                                    |
| K25.4  | Chronic or unspecified gastric ulcer with hemorrhage                                        |
| K25.6  | Chronic or unspecified gastric ulcer with both hemorrhage and perforation                   |
| K26.0  | Acute duodenal ulcer with hemorrhage                                                        |
| K26.2  | Acute duodenal ulcer with both hemorrhage and perforation                                   |
| K26.4  | Chronic or unspecified duodenal ulcer with hemorrhage                                       |
| K26.6  | Chronic or unspecified duodenal ulcer with both hemorrhage and perforation                  |

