## Appendix A

|         |                                                                                               |
|---------|-----------------------------------------------------------------------------------------------|
| K57.31  | Diverticulosis of large intestine without perforation or abscess with bleeding                |
| K57.33  | Diverticulitis of large intestine without perforation or abscess with bleeding                |
| K57.41  | Diverticulitis of both small and large intestine with perforation and abscess with bleeding   |
| K57.51  | Diverticulosis of both small and large intestine without perforation or abscess with bleeding |
| K57.53  | Diverticulitis of both small and large intestine without perforation or abscess with bleeding |
| K57.81  | Diverticulitis of intestine, part unspecified, with perforation and abscess with bleeding     |
| K57.91  | Diverticulosis of intestine, part unspecified, without perforation or abscess with bleeding   |
| K57.93  | Diverticulitis of intestine, part unspecified, without perforation or abscess with bleeding   |
| K62.5   | Hemorrhage of anus and rectum                                                                 |
| K63.1   | Perforation of intestine (nontraumatic                                                        |
| K63.81  | Dieulafoy lesion of intestine                                                                 |
| K66.1   | Hemoperitoneum                                                                                |
| K92.0   | Hematemesis                                                                                   |
| K92.1   | Melena                                                                                        |
| K92.2   | Gastrointestinal hemorrhage, unspecified                                                      |
| M25.00  | Hemarthrosis, unspecified joint                                                               |
| M25.011 | Hemarthrosis, right shoulder                                                                  |
| M25.012 | Hemarthrosis, left shoulder                                                                   |
| M25.019 | Hemarthrosis, unspecified shoulder                                                            |
| M25.021 | Hemarthrosis, right elbow                                                                     |
| M25.022 | Hemarthrosis, left elbow                                                                      |

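### As printed, the six-month gastrointestinal-bleeding exclusion omits K25.4x and takes in diverticular codes that the Major Bleeding sheet does not count as bleeds; the effect is small, but the lists need reconciling

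*Combined protocol and SAP*

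**What the plan says.** **The exclusion (Appendix A, Exclusion criteria, gastrointestinal bleeding, 6 months).** It looks back 180 days including the day of initiation, in any diagnosis position, inpatient only. The ICD-10 part starts "K25.0x, K25.2x, K25.6x, K26.0x, K26.2x, K26.4x, K26.6x". It then gives the same four suffixes for K27 and continues "K28.0x, K28.2x, K28.4x, K28.6x, K55.21, K57.xx, K62.5x". The ICD-9 part lists 531.0x, 531.2x, 531.4x and 531.6x, the matching codes for 532 to 534, and then "562.0x, 562.1x, 568.8x, 569.3x, 569.8x".

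**The Major Bleeding sheet (Appendix A).** This sheet lists K25.4 as "Chronic or unspecified gastric ulcer with hemorrhage". Its K57 entries are individual codes that all carry a bleeding label, for example K57.31, "Diverticulosis of large intestine without perforation or abscess with bleeding". Its ICD-9 diverticular entries are 562.02, 562.03, 562.12 and 562.13, all labelled as hemorrhage, for example "DIVERTICULOSIS OF COLON WITH HEMORRHAGE".

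**Neighbouring rules.** The overt-major-bleeding exclusion applies the whole Major Bleeding sheet, inpatient or outpatient, on the day before and the day of initiation. The bleeding-risk exclusion requires HAS-BLED of 3 or more over 30 days. A note at the head of Appendix A says that the full ICD-10 lists are kept in an external folder.

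**Use of the outcome.** Major bleeding is the assay-sensitivity endpoint (Section 1.5) and the safety outcome (Section 6.3.1). Follow-up starts the day after initiation (Section 6.3.2).

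**The concern.** One criterion appears to be wrong in two opposite directions.

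A chronic or unspecified gastric ulcer bleed treated in hospital four months before initiation excludes the patient if coded 531.4x, but not if coded K25.4. The clinical history is the same and the code system decides eligibility. K25.4 is also an outcome code, so a patient let in this way could later have a claim for the same ulcer counted as an on-treatment bleed.

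Conversely, the criterion is headed as bleeding, but a secondary diverticular diagnosis on any inpatient stay is enough to exclude, whether or not there was a bleed. The Major Bleeding sheet shows that the authors separated bleeding from non-bleeding diverticular codes elsewhere in the same appendix.

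**Working it through.** **1. Ulcer-with-hemorrhage codes, exclusion against sheet.**

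| Family | Exclusion, ICD-10 | Major Bleeding sheet |
|---|---|---|
| K25 | .0, .2, .6 | .0, .2, .4, .6 |
| K26 | .0, .2, .4, .6 | .0, .2, .4, .6 |
| K27 | .0, .2, .4, .6 | .0, .2, .4, .6 |
| K28 | .0, .2, .4, .6 | .0, .2, .4, .6 |

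Fifteen of 16 groups are present.

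**2. All gastrointestinal codes on the sheet, matched by prefix to the exclusion.** The sheet has 37 ICD-10 codes beginning with K. Two are not matched: K25.4 and K56.60. The sheet labels K56.60 as intestinal obstruction, so K25.4 is the only gastrointestinal hemorrhage code missed. No ICD-9 gastrointestinal code is missed, reading the sheet's undecimalised 531 to 534 and 578 entries as the .0 codes that their labels describe.

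**3. Breadth of the wildcards.**

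| Exclusion | Sheet |
|---|---|
| K57.xx | 12 codes, all labelled with bleeding |
| 562.0x | 562.02, 562.03 |
| 562.1x | 562.12, 562.13 |
| 568.8x | 568.81 |
| 569.8x | 569.83, 569.85, 569.86 |

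That the diverticular wildcards contain non-bleeding codes is inferred from the sheet's selective labels. The documents do not print those codes.

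**4. Window left open for an inpatient K25.4.**
- Days -1 and 0: caught by the overt-major-bleeding exclusion.
- Days -30 to -2: caught only if HAS-BLED reaches 3.
- Days -180 to -31: no specific rule catches it.

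**5. Size of the step (Section 5.3, Exclusion 11.3).** The plan's figures reproduce:
- Optum: 4,660 - 12 = 4,648 (0.26% removed).
- MarketScan: 6,750 - 52 = 6,698 (0.77%).
- Medicare: 9,189 - 78 = 9,111 (0.85%).
- Total: 12 + 52 + 78 = 142 of 4,660 + 6,750 + 9,189 = 20,599, or 0.69%.

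The 142 include true bleeders, so this is an upper bound on non-bleeders dropped at this step.

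**6. Power.** Section 10's pooled figure reproduces from Phi(sqrt(D/4) × ln(1.8/0.84) - 1.96).
- As planned: D = 7,140 × 13.74/1,000 = 98.10, giving 0.9652.
- With all 142 restored and matched at the present fraction of the final cohort (4,264 + 6,338 + 8,400 = 19,002): 7,140 × (1 + 142/19,002) = 7,193 patients, D = 98.8, power 0.966.

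**7. Upper gastrointestinal bleeders left in the cohort (Appendix B).** Before matching, every cell of the upper GI bleed row is suppressed as below 11, so each arm in each database has at most 10. After matching the row reads 0 and 0 in Optum, 0.1% and 0.1% in MarketScan, and 0.2% and 0.1% in Medicare. Undoing the rounding:
- 0.1% of 1,381 is 1 or 2 patients, in each MarketScan arm.
- 0.2% of 1,699 is 3 or 4, and 0.1% is 1 or 2, in Medicare.
- Total: 6 to 10 of 7,140, with standardized differences of 0.00 (MarketScan) and 0.03 (Medicare).

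This assumes that the covariate captures gastric-ulcer hemorrhage; its code list is not printed.

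**The case against.** The strongest reply is that the printed cell may not be what was run. Appendix A says that the full ICD-10 lists sit elsewhere and were produced by mapping from ICD-9, and 531.4x is in the ICD-9 list. A transcription slip is as plausible as a real gap. This stands, and it limits the point to the printed text until the archived list is checked.

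A reader might infer that the major-bleeding comparison is contaminated by recent K25.4 bleeders. The documents do not support that. Active bleeding at initiation is caught on days -1 and 0, few upper gastrointestinal bleeders are visible after matching, and they are balanced. Nor is carry-over of an earlier bleed peculiar to K25.4. The final unmatched cohort keeps 114 + 106 = 220 patients with a lower or unspecified gastrointestinal bleed at baseline, and adding K25.4x would not change the rules that let them in.

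A reader might also infer that the wildcards bias the treatment comparison. They apply identically to both arms before matching. The trial criterion concerns conditions in which serious bleeding may occur, so a broad list can be defended as cautious. What remains is that the list is wider than its own label and than the plan's own definition of a diverticular bleed, and the plan gives no reason for this.

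**Conclusion.** The inconsistency holds for the printed plan. K25.4x is missing where three parallel ICD-10 families, the ICD-9 counterpart and the plan's own bleeding sheet all point to its inclusion. The diverticular wildcards are broader than the sheet. Followed as written, the list misclassifies eligibility in both directions and makes it depend on the code system.

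The consequence is minor. Cohort size and power are essentially unaffected, and no bias in the bleeding endpoint is shown. The number of K25.4 patients retained, and the share of the 142 who had no bleed, cannot be derived because there are no per-code counts. The conclusion rests on the printed list being the one implemented; if it was not, only the text is wrong. The case for acting is correct eligibility, fidelity to the trial's six-month criterion, and consistency between ICD-9 and ICD-10.

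**What to change.** 1. Compare the implemented Exclusion 11.3 list with the list printed in Appendix A, and state which governs.
2. Add K25.4x.
3. Replace K57.xx, 562.0x and 562.1x with the 12 ICD-10 and four ICD-9 diverticular codes on the Major Bleeding sheet.
4. Narrow 568.8x to 568.81, and 569.8x to 569.83, 569.85 and 569.86. Code 569.83 is intestinal perforation, as is K63.1x, which is already in the exclusion. Keep both or drop both: restricting 569.8x to hemorrhage-labelled codes alone would remove 569.83 while K63.1x stays, which creates a new mismatch between the code systems.
5. If the implemented list changes, rerun the flowchart from the Exclusion 11.3 row, then the matching, balance and power tables that follow from it.

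The cost is a code-list edit and at most one rerun. If only the printed text is wrong, correcting the text is enough. Section 13 is still blank, so on this record the change would precede the comparative results.

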# Appendix A

|                                                                                                                                                                                                                                                                                                                                                                                                                                                         |                                                                                                                                                                                                                                                                                                                                                                                                                                                              |  |  |
|---------------------------------------------------------------------------------------------------------------------------------------------------------------------------------------------------------------------------------------------------------------------------------------------------------------------------------------------------------------------------------------------------------------------------------------------------------|--------------------------------------------------------------------------------------------------------------------------------------------------------------------------------------------------------------------------------------------------------------------------------------------------------------------------------------------------------------------------------------------------------------------------------------------------------------|--|--|
| 
- Intracranial neoplasm, arteriovenous malformation or aneurysm
                                                                                                                                                                                                                                                                                                                                                                                  | 
Measured 1 day prior to and including the day of drug initiation in any diagnosis position and in an inpatient or outpatient care setting
 
Intracranial neoplasm:
ICD-9 Dx: 239.6x, 191.xx, 225.xx
ICD-10 Dx: D49.6x, C71.x, D33.0x, D33.1x, D33.2x
 
AV malformation of brain:
ICD-9 Dx: 747.81
ICD-10 Dx: Q28.2x, Q28.3x
 
Cerebral aneurysm
ICD-9 Dx: 437.3x
ICD-10 Dx: I67.1x
 |  |  |
| 
- Overt major bleeding
                                                                                                                                                                                                                                                                                                                                                                                                                           | 
Measured 1 day prior and including the day of drug initiation in any diagnosis position and in an inpatient or outpatient care setting
 
See 'Major Bleeding' sheet for codes
                                                                                                                                                                                                                                                             |  |  |
| 
- Documented hemorrhagic tendencies or blood dyscrasias
                                                                                                                                                                                                                                                                                                                                                                                          | 
Measured 1 day prior and including the day of drug initiation in any diagnosis position in an inpatient or outpatient care setting
 
Coagulation defects
ICD-9 Dx: 286.x
ICD-10 Dx: D65.x, D66.x, D67.xx, D68.xx, D69.xx
 
Malignant Neoplasm Of Lymphatic And Hematopoietic Tissue
ICD-9 Dx: 200.xx to 209.xx
ICD-10 Dx: C81.xx to C96.xx
                                                             |  |  |
| 
Active and clinically significant liver disease (eg, hepatorenal syndrome)
                                                                                                                                                                                                                                                                                                                                                                       | 
Measured 180 days prior to and including the day of drug initiation in any diagnosis position and in an inpatient or outpatient care setting
 
Liver disease
ICD-9 Dx:
070.xx, 570.xx-573.xx
456.0x-456.2x, 576.8x, 782.4x, 789.5x
ICD-9 Px:
39.1x, 42.91
 
Hepatorenal syndrome
ICD-9 Dx: 572.4
ICD-10 Dx: K76.7
                                                                          |  |  |
| 
Life expectancy <6 months
                                                                                                                                                                                                                                                                                                                                                                                                                     | 
Measured 180 days prior to drug initiation in any diagnosis position and in an inpatient or outpatient care setting
 
CCI>=10
                                                                                                                                                                                                                                                                                                          |  |  |
| 
Bacterial endocarditis
                                                                                                                                                                                                                                                                                                                                                                                                                           | 
Measured 180 days prior to and including the day of drug initiation in any diagnosis position and in an inpatient or outpatient care setting
 
Bacterial endocarditis
ICD-9 Dx: 421.0x
ICD-10 Dx: I33.0x
                                                                                                                                                                                                                   |  |  |
| 
Uncontrolled hypertension: systolic blood pressure >180 mm Hg or diastolic blood pressure >100 mm Hg; (subjects who have a transient, higher blood pressure elevation associated with acute PE [upper limit: systolic blood pressure 200 mm Hg or diastolic blood pressure 100 mm Hg] may enter the study;) elevated blood pressure that is persistent 1-2 days after the index DVT or PE should be treated according to local guidelines.
 | 
Measured 180 days prior to and including the day of drug initiation in any diagnosis position and in an inpatient or outpatient care setting
 
Malignant hypertension
ICD-9 Dx: 401.0x
 
Hypertensive urgency/ Hypertensive crisis
ICD-10 Dx : I16.xx
                                                                                                                                                          |  |  |
| 
Platelet count <100,000/mm^3
                                                                                                                                                                                                                                                                                                                                                                                                        | 
Measured 180 days prior to and including the day of drug initiation in any diagnosis position and in an inpatient or outpatient care setting
 
Thrombocytopenia
ICD-9 Dx: 287.3x, 287.4x, 287.5x
ICD-10 Dx: D69.3x, D69.4x, D69.5x, D69.6x
                                                                                                                                                                                 |  |  |

